Study protocol with statistical analysis plan

Fostering Sustainable Dietary Habits Through Optimized School Meals
- an intervention study in Uppsala, Sweden

Date: January 21, 2020

Introduction

Radical changes to food production and consumption are needed to ensure the attainment of Agenda 2030 for Sustainable Development and fulfillment of the Paris Agreement (1). Public school meals have been highlighted as a suitable setting for children to internalize sustainable dietary habits, which may persist throughout life (2). Planning of school meals must take many aspects into account: health promotion, environmental impact, acceptability by the consumers and affordability to those paying for the meals. Currently many schools use organic products, recycle food packaging and aim to reduce food waste, but environmental impacts like greenhouse gas emissions (GHGE) have so far not received much attention.

In Sweden, fully subsidized lunches are served daily in primary schools to all 1.3 million children aged 6 to 15 (3). Due to their reach and scale (approximately 230 million meals/year at an annual cost of around 6 billion SEK), school meals have great potential to increase children's knowledge about health and sustainability, foster sustainable dietary habits and to enable sustainable public procurement.

This study builds on a previously published strategy for how to optimize, plan and implement nutritiously adequate, affordable, acceptable and more climate friendly meals in Swedish primary schools (4). In line with this strategy, the present study aims to: a) Apply linear programming to develop a GHGE-reduced, nutritionally adequate, and affordable four-week lunch menu plan optimized for minimum deviation from the current food supply; and b) evaluate the climate impact of the menu, effects on food waste, food consumption, and pupils' satisfaction with school lunches. Our hypothesis is that school meals can be optimized to be nutritious and more climate friendly, without negatively affecting acceptance, food waste and cost in this context.

Methods

Design

A pre-post design will be used to compare the effect of an optimized menu to the baseline menu on daily food waste and consumption at school level. For a baseline period of four weeks children in primary schools will receive a baseline menu. After a one-week break (winter break), the optimized four-week menu will be served (intervention period).

Recruitment of schools

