Data on school meal satisfaction will also be collected through an anonymous online questionnaire at baseline and during the last week of the intervention period. Pupils in grades 5 and 8 will answer the questionnaire containing ten questions related to the school lunch. Five of the ten multiple-choice questions specifically cover their general (i.e. not for that specific day of week) sense of satisfaction with the school lunch. The questions include how often they consider that the school lunch tastes good, how many days per week on average they eat it, how often they usually feel full after having eaten lunch, and how often they throw away food. They are also asked to provide an overall rating of the school lunch.

Statistical analysis

A pre-post design will be employed to assess the effect of implementing an optimized lunch menu on daily food waste and consumption at school level. Data will be analyzed by interrupted time series analysis assessing mean and slope differences in daily food waste and consumption between the two periods (6). School lunch satisfaction before and after introduction of the new menu plan will be compared by means of Pearson's χ^2 test.

References

3. The National Food Agency; The Swedish National Agency for Education. *Skolmältiden – en viktig del av en bra skola. (The school meal: an important part of a good school: support and inspiration for school leaders)*. Uppsala, Stockholm; 2013.
5. Floren B, Amani P, Davis J. Climate Database Facilitating Climate Smart Meal Planning for the Public Sector in Sweden. *Int J Food Syst Dyn*.8:72–80.

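### Ordered satisfaction items are compared only by Pearson's chi-square, which ignores order and direction, and no estimate of the change is planned

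*Combined protocol and SAP*

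**What the plan says.** The Outcomes section describes "an anonymous online questionnaire at baseline and during the last week of the intervention period", and adds: "Pupils in grades 5 and 8 will answer the questionnaire containing ten questions related to the school lunch". Half of these multiple-choice items concern general satisfaction. Three of them are frequencies: "how often they consider that the school lunch tastes good", the frequency of feeling full afterwards, and the frequency of throwing food away. A fourth asks for the usual number of days per week on which pupils eat the lunch. Of the fifth item the section says: "They are also asked to provide an overall rating of the school lunch".

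The whole analysis plan for these items, under Statistical analysis, is: "School lunch satisfaction before and after introduction of the new menu plan will be compared by means of Pearson's χ^2 test". The document names no ordinal or trend method, effect measure, confidence interval or rule for collapsing categories. It does not give the number of answer options or of pupils, or say whether school and grade are recorded with the answers.

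The Introduction includes pupils' "satisfaction with school lunches" in aim (b) and states the hypothesis that meals can be improved "without negatively affecting acceptance, food waste and cost in this context". The Outcomes section lists plate waste (total and per pupil), serving waste and consumption (total and per pupil) as primary. Satisfaction is not among them.

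**The concern.** Three items are frequencies, one is a number of days per week and one is a rating, so all five have a natural order. The question of interest has a direction: did satisfaction get worse? Pearson's chi-square on the uncollapsed table spreads its sensitivity over every possible pattern of difference. It has less chance of detecting a consistent shift along the scale, and its value does not show which way answers moved.

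At stake is the reading of a result that is not significant. With no planned estimate or interval, such a result could be reported as showing that satisfaction was unaffected when the data are also compatible with a real fall.

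**Working it through.** The documents give no sample size, power or answer distribution for satisfaction, so there is no planned figure to reproduce. All counts, shares and effect sizes below are assumptions.

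**1. Direction and size: a worked table.** Assume 300 answers per round on a five-point item.
- Before: 30/60/120/60/30, mean 900/300 = 3.00.
- After, a fall: 40/72/118/48/22, mean 840/300 = 2.80.
- After, a rise: 22/48/118/72/40, mean 960/300 = 3.20.

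With equal round sizes, Pearson's statistic is the sum over categories of (before − after)² / (before + after). For the fall: 100/70 + 144/132 + 4/238 + 144/108 + 64/52 = 1.429 + 1.091 + 0.017 + 1.333 + 1.231 = 5.10, 4 df, p = 0.28. The rise gives the same five terms in reverse order, so again 5.10 and p = 0.28.

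The row-mean-score statistic is d² / [V(1/300 + 1/300)], where V is the pooled score variance, 1.205. With d = ±0.20 this is 0.04/0.00804 = 4.98, 1 df, p = 0.026 in both cases.

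The shift has standard error √(1.204/300 + 1.191/300) = 0.0893. The 95% CI is −0.20 ± 1.96 × 0.0893, or −0.375 to −0.025, for the fall and 0.025 to 0.375 for the rise. The interval separates the two cases. Pearson's p-value does not.

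**2. General cost of the extra degrees of freedom.** Suppose the change lies wholly along the order and a 1-df test has 80% power (noncentrality 7.85). The omnibus test then has 71% power with 2 df, 64% with 3 and 60% with 4. To reach 80% it needs about 1.23, 1.39 or 1.52 times the sample.

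**3. Simulated power.** Assumptions: shares before of 10/20/35/25/10%, a latent normal scale, a drop of 0.2 SD, independent rounds, no variation between schools in the change, two-sided 5% level. Each cumulative share c becomes Φ(Φ⁻¹(c) + 0.2), which moves the top two options from 35% to 28%.

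| Pupils per round | Pearson | Ordinal |
|---|---|---|
| 200 | 29% | 47% |
| 300 | 42% | 64% |
| 400 | 56% | 77% |

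Type I error is near 5% for both tests here. A non-significant Pearson result is therefore the more likely one at 200 and 300 pupils, but not at 400.

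**4. What changes the gap (300 per round).** At a drop of 0.3 SD it is 81% versus 94%. With three options and 0.2 SD it is 46% versus 57%. With items collapsed to two categories the two methods are the same test, at about 44–47%.

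**5. Schools that change differently.** Assume the change varies between the four schools with an SD of 0.2 on the latent scale, at 300 pupils per round. Simulated type I error is then 15–24% for the ordinal test and 9–16% for Pearson, and the 95% CI for the shift covers 79–85%. At an SD of 0.1 the type I errors are 4–10% and 3–7%, with coverage of 90–96%. The ranges cover 0–100% of pupils answering twice.

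**The case against.** A reader might infer that Pearson's test is the wrong test, or invalid. The documents do not support that: for independent answers it holds its type I error, and it can detect polarisation (more answers at both extremes), which an ordinal test may miss.

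A reader might also infer that changing the test would allow a conclusion of no harm. It would not. A non-significant ordinal test shows absence of harm no better than a non-significant Pearson test. That gap comes from the missing estimate and interval, whichever test is used.

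Nor can it be said without limit that Pearson would probably miss a 0.2 SD fall. At 400 pupils per round it would more often detect it. The documents give neither pupil numbers nor answer options, so the actual loss of power cannot be established, and 0.2 SD is an illustrative fall, not a margin from the plan.

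The ordinal test is also the more exposed of the two if the four schools change differently. Direction would be visible in the percentages behind the chi-square table, although the plan does not commit to showing them. Finally, the Outcomes section ties acceptability to the waste and consumption outcomes, so the hypothesis does not rest on the questionnaire alone.

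All of this stands, and it limits the point. It does not remove it: satisfaction is a named aim, order and direction are ignored whatever the pupil numbers as long as items stay uncollapsed, and no estimate of change is planned.

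**Conclusion.** The point holds as a matter of lost sensitivity and interpretability, not of validity. Two parts need no assumed figures: on uncollapsed items the planned test cannot tell a fall from its mirror-image rise, and the plan names no estimate or interval for the change. The loss of power is conditional: about 18 to 22 percentage points at 200–400 pupils per round (47 − 29 = 18, 64 − 42 = 22, 77 − 56 = 21), given five options, independent rounds, a 0.2 SD drop and no difference in change between schools. It is about 11 points with three options (57 − 46) and nil with two. The change is worth making, but importance is modest because satisfaction is not a primary outcome.

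**What to change.** 1. For each item, report the category percentages in both rounds and the before-after shift with a 95% CI. State that a non-significant result of any test will not be read as no harm. This is the main change.
2. Name an ordinal comparison (proportional-odds model or row-mean-score test) as the preferred test, stratified by school and grade if these are recorded with the answers. Pearson's test may stay beside it to pick up polarisation.
3. Next to this, state two limits. With four schools, the ordinal test and its interval are too optimistic if schools change differently, more so than Pearson. The same grades answer both anonymous rounds, so pupils who answer twice cannot be paired. If school is recorded, show the shift in each of the four schools.

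The cost is a few lines of SAP text and slightly more analysis, with no new data. The trade-off is less sensitivity to changes without a net shift, which is why the percentages must be shown, and more sensitivity to differences between schools in the change.

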During the fall of 2019, a meeting was held with the public meal administration in the municipality of Uppsala. The research team described the OPTIMAT project, including the previously developed strategy for optimizing and implementing more climate friendly lunches in schools (4). Following this meeting, the municipality agreed to take part in the project. The municipality's meal planner proposed four primary schools for the study, presently having the highest food related GHGE in public meals in the municipality. To be eligible, the intervention schools were required to have on-site kitchens as well as being able to provide electronic recipes for a standard four-week menu. All proposed schools fulfilled these criteria and approved participation.

Optimization

Recipes for an original (baseline) four-week school lunch menu plan previously served at the recruited schools were obtained through the municipality's electronic meal planning system. The foods included and amounts are considered as the baseline food supply. Each food item included has a code that can be coupled to the Swedish national food database and a national climate database for foods containing life cycle data for each food item (5). This baseline food supply will be optimized using linear programming. The optimized food list, not including new foods or excluding any foods from the baseline list, will be handed to the municipality's meal planner who develops a new menu plan for the intervention using all foods on the optimized list.

Outcomes

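### The before-after satisfaction test is not stratified by school or grade, so a change in who answers the anonymous questionnaire can be mistaken for, or can mask, a change in satisfaction

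*Combined protocol and SAP*

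**What the plan says.** The Introduction puts satisfaction into aim b, which covers "effects on food waste, food consumption, and pupils' satisfaction with school lunches". Under Recruitment of schools, the municipality's "meal planner proposed four primary schools for the study", and all four agreed to take part.

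Under Outcomes, satisfaction data are "collected through an anonymous online questionnaire at baseline and during the last week of the intervention period". On who answers: "Pupils in grades 5 and 8 will answer the questionnaire containing ten questions related to the school lunch". On content: "Five of the ten multiple-choice questions specifically cover their general" satisfaction with the school lunch.

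Under Statistical analysis, the only text on this outcome is "School lunch satisfaction before and after introduction of the new menu plan will be compared by means of" Pearson's chi-square test. The interrupted time series analysis and the references to school level concern daily food waste and consumption only.

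Nowhere do the documents mention, for the questionnaire:
- stratification or adjustment by school or grade;
- recording school and grade with the answers;
- response numbers per round;
- any comparison of who answered in each round.

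**The concern.** A before-after Pearson test with no further qualification has one dimension for round and one for answer. Every respondent in a round counts equally, whatever the school or grade. The combined percentage is therefore a weighted average of the group percentages, with weights set by who happened to answer. If a class misses the last intervention week, or one grade responds less the second time, the weights change. If the groups also rate lunch differently, the combined percentage moves although no group has changed its view.

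The error can go either way. If the less satisfied group responds less at follow-up, the combined figure rises and can hide a real fall. That error favours the study hypothesis that acceptance does not suffer. If the more satisfied group responds less, the menu is blamed for a fall that did not happen. Combining the groups can also cancel opposite changes in grades 5 and 8.

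The choice has to be made before the first round. If school and grade are not captured in an anonymous survey, they cannot be recovered afterwards.

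**Working it through.** **No figure to reproduce.** The documents give no pupil numbers, response rates, satisfaction levels, significance level or power for the questionnaire. What follows is an illustration on assumed inputs.

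**Inputs**
- From the documents: four schools; grades 5 and 8; two anonymous rounds; Pearson's test.
- Assumed: all four schools have both grades, giving 4 × 2 = 8 groups; 40 answers per group at baseline; answers reduced to favourable or not; favourable shares of 70, 65, 65 and 60% in grade 5 (mean 65%) and 50, 45, 45 and 40% in grade 8 (mean 45%); grade 5 responds fully both times; rounds independent; two-sided 5% level.

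**Step 1: shift with no true change.** Combined share = (n5 × 0.65 + n8 × 0.45) / (n5 + n8).
- Baseline: (160 × 0.65 + 160 × 0.45) / 320 = 0.550
- Grade 8 at 90%: (104 + 144 × 0.45) / 304 = 0.555, shift +0.5 points
- Grade 8 at 80%: (104 + 128 × 0.45) / 288 = 0.561, shift +1.1 points
- Grade 8 at 60%: (104 + 96 × 0.45) / 256 = 0.575, shift +2.5 points
- Grade 8 at 40%: (104 + 64 × 0.45) / 224 = 0.593, shift +4.3 points

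**Step 2: what the test does.** Simulation under the same model compared the unstratified Pearson test with a Cochran-Mantel-Haenszel (CMH) test over the eight groups.

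| Grade 8 response at follow-up | False positives, unstratified | Power for a 10-point fall, unstratified | Power for a 10-point fall, CMH |
|---|---|---|---|
| 100% | about 5% | 73% | 73% |
| 90% | about 5% | 66% | 72% |
| 80% | about 5% | 59% | 71% |
| 60% | about 9% | 43% | 68% |
| 40% | about 16% | 26% | 63% |

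CMH false positives stay at about 5% throughout. A true 5-point fall in every group appears as -5.0 + 2.5 = -2.5 points at 60% response and -5.0 + 4.3 = -0.7 points at 40%. The stratified estimate stays at -5.0.

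**Step 3: precision.** The standard error of the difference is 4.1 points either way at 60% response. At 40% it is 4.3 points stratified against 4.2 unstratified.

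**Step 4: other assumptions.** Take 400 answers per round, 70% favourable in grade 5 and 50% in grade 8, stratified by grade only.
- Grade 5 share of answers falls from 50% to 35%, no true change: the combined figure goes from 0.50 × 70 + 0.50 × 50 = 60% to 0.35 × 70 + 0.65 × 50 = 57%. False positives are 12.9% unstratified and 4.9% stratified.
- True 10-point fall in both grades, grade 5 share rises from 50% to 70%: the combined figure is 0.70 × 60 + 0.30 × 40 = 54%, so the fall looks like 6 points. Power is 39.7% unstratified and 81.4% stratified.
- Small change, grade 5 share from 50% to 45%, grade gap 10 to 30 points: false positives are only 5.2% to 7.2% (normal approximation).

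**The case against.** **Combining the groups is inferred.** A reader might take the plan to prescribe one test on a single table over all schools and grades. It does not say so. Five satisfaction questions imply about five tests, and nothing excludes running them by grade or school. This stands as a matter of wording: the gap is one of specification. Combining remains the natural reading of an unqualified Pearson test, and if separate tests are intended, the plan needs to say that.

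**Both conditions for bias are assumed.** The same grades in the same schools are surveyed twice within about nine weeks (four, a one-week break, four), so the intended mix is the same. The documents do not show that response will change, that grades differ in satisfaction, or that every school has both grades. This also stands. A reader might infer that the planned result will be biased; the documents support only that it could be, and that no check is planned.

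**Mild loss does little harm.** At 90% or 80% grade 8 response, false positives stay near 5%. That is correct, although power already drops from 72% to 66% and from 71% to 59%.

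**The rounds are probably not independent.** Many pupils are likely to answer twice, which makes both tests conservative. With an assumed within-pupil correlation of 0.5, unstratified false positives at 60% and 40% response are 5.1% and 12.1%; at 0.7 they are 3.4% and 10.3%. The false-positive figures above are therefore on the high side. The shift in the estimate, and the masking of a fall, remain.

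**Satisfaction is not primary.** The five primary outcomes come from kitchen weighing and are themselves presented under Outcomes as reflecting acceptability. The conclusion on acceptance does not rest on the questionnaire alone.

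**Conclusion.** The concern holds in conditional form. As written, the satisfaction comparison has no protection against a change in the school and grade mix of respondents, and the plan provides no means of detecting one. The effect needs both a changed mix and a difference in satisfaction between groups. On the assumed inputs it runs from negligible (0.5 points at 90% grade 8 response) to serious (4.3 points at 40%, with power for a 10-point fall at 26% against 63% stratified). All these sizes rest on assumed group sizes, an assumed 20-point grade gap and independent rounds.

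A reader might go further and infer that the study's main conclusions are compromised. The documents do not support that. The point concerns the satisfaction part of aim b and leaves the primary waste and consumption analyses untouched. It is still worth acting on, because the questionnaire is the only direct report from pupils and stratifying costs almost nothing if the mix proves stable.

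**What to change.** 1. Record school and grade with each answer in both rounds, by one extra item or a separate link per school and grade. Neither identifies a pupil.
2. Replace the unstratified Pearson test with a comparison stratified by school and grade: Cochran-Mantel-Haenszel, or ordinal or logistic regression with school and grade terms. State that it applies to each satisfaction item.
3. Report response numbers per round by school and grade, and show results by grade and by school, so that opposite changes are visible.

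**Cost.** A sentence or two in the plan, one item or up to eight links, and practically no precision: with equal response in both rounds, power is 73.1% unstratified and 73.5% stratified in the example.

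**What it leaves open.** Stratifying does not remove selective response within a school and grade, such as dissatisfied pupils skipping the second round. Nor does it deal with dependence between rounds when the same pupils answer twice. Both should be acknowledged when the result is reported.
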